Following initial screening and a 1-week enrolment period, patients will enter a 4-week placebo lead-in period, after which they will be randomised to the 16-week double-blind treatment period. After either completion of the randomised treatment period or early discontinuation from treatment, patients will enter a 4-week follow-up period.

The total planned study duration starting with enrolment and including the follow-up period will be 25 weeks.

Outcome variable(s):

Primary outcome variable:

- Change in HbA1c from baseline to week 16

Key secondary outcome variables:

- Percent change in body weight from baseline to week 16
- Change in FPG from baseline to week 1
- Change in FPG from baseline to week 16
- Proportion of patients with HbA1c<7.0% at week 16, in patients who had HbA1c \geq 7.0% at baseline.

Other secondary outcome variables:

- Change in seated systolic and diastolic blood pressure (BP) from baseline to week 16
- Proportion of patients with seated systolic blood pressure <130 mmHg at week
 16 in patients who had seated systolic blood pressure ≥130 mmHg at baseline
- Change in body weight from baseline to week 16

The following secondary outcome variables apply to dapagliflozin 10 mg only:

- Change in HbA1c from baseline at week 16
- Change in FPG from baseline at week 1 and 16
- Proportion of patients with HbA1c<7.0% at week 16, in patients who had HbA1c \geq 7.0% at baseline

- Percent change in body weight from baseline to week 16
- Change in body weight from baseline to week 16
- Change in seated systolic and diastolic blood pressure (BP) from baseline to week 16
- Proportion of patients with seated systolic blood pressure <130 mmHg at week
 16 in patients who had seated systolic blood pressure ≥130 mmHg at baseline

Safety

Adverse Events (AE) laboratory values, electrocardiogram, pulse, blood pressure, hypoglycaemic events, cardiovascular events, calculated creatinine clearance, estimated glomerular filtration rate and physical examination findings.

Statistical methods

The primary outcome variable, change from baseline to week 16 in HbA1c, will be analyzed by an analysis of covariance (ANCOVA) model which will include terms for treatment group and covariate for baseline HbA1c. The ANCOVA model will be used to derive a least squares estimate of the treatment difference with 95% confidence interval and corresponding 2-sided p-value.

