3.1.1.4 Randomisation and Double-blind Treatment Period (Visits 4-9, week 0 to week 16)

Randomisation visit (Visit 4, week 0)

Eligible patients will be randomised at Visit 4 (week 0, baseline) in a 1:1:1:1 ratio to receive either dapagliflozin 2.5 mg BID, or dapagliflozin 5 mg BID, or dapagliflozin 10 mg QD, or placebo. At Visit 3, one week before randomisation, patients will be stratified based on 1 recruitment factor:

Factor 1: HbA1c value (determined in the blood sample taken at Visit 3, one week before randomisation).

- Stratum 1 (HbA1c <7.0% at randomisation)
- Stratum 2 (HbA1c \geq 7.0% at randomisation)

Stratum 1 is planned to be a maximum of 20% of the randomised patients. If the number of patients in Stratum 1 reaches 20% (n=78) of the total number of planned randomised patients (20% of 392 anticipated is: 78 patients), communication will be sent out to all sites that screening and enrolment will only continue for patients in Stratum 2 with an HbA1c \geq 7.2% and <10.5% (see Section 4.1, inclusion criterion no. 5, Note 1). For these patients in Stratum 2, the randomisation criterion for HbA1c \geq 7.0% and <10.0% will apply (see Section 4.1 inclusion criterion no. 6, Note 2).

Maintenance Treatment Period (Visits 5-9)

Patients will follow up at week 1 (Visit 5), week 4 (Visit 6), week 8 (Visit 7), week 12 (Visit 8) and week 16 (Visit 9) after randomisation, completing the randomised treatment period.

Patients will continue to monitor their FPG levels at least every second day and will continue to enter the results into the patient diary. Investigators may instruct patients to monitor their FPG more often, according to their local treatment guidelines or clinical judgement. Hypoglycaemic events should also be entered into the patient diary. For FPG monitoring procedures and assessment of hypoglycaemic events please refer to Section 6.4.10.1. Diet and lifestyle modification will be reinforced at each visit during the double-blind treatment period.

The following table displays criteria for lack of glycaemic control during the double-blind treatment period. For Visit 6 measurement FPG >240 mg/dL (13.2 mmol/L), and for Visit 8 measurement FPG >200 mg/dL (11.1 mmol/L) will be considered as threshold. Subjects who lack glycaemic control as defined below will be discontinued from the study and will have follow up visit procedures performed. Up-titration of metformin dose during the study will not be allowed.

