A patient that discontinues will always be asked about the reason(s) for discontinuation and the presence of any AEs. If possible, they will be seen and assessed by an investigator(s). AEs will be followed up (See Sections 6.4.1 and 6.4.4); patient diaries and study drug should be returned by the patient.

Randomised patients

Randomised patients who discontinue the study before week 16 should return and complete the procedures described for Visit 9 as soon as possible but at the latest 7 days after discontinuation. These patients should also be scheduled for a follow-up visit (ie, procedures of Visit 10) four weeks after discontinuation of investigational product. In addition the investigator should follow patients who discontinue the study due to an AE including a laboratory abnormality until the event has been resolved or stabilised.

After discontinuation of investigational product and open-label metformin, alternative antihyperglycaemic treatment should be considered according to the investigator's judgement and according to local medical practice.

Patients with an increased CK >10xULN will have their investigational product withheld and repeated CK test preferably within 24 hours, but not exceeding 72 hours. If repeated CK is still >10xULN the patient should permanently discontinue study medication and be withdrawn from the study (in which case an Adverse Event must be reported). Otherwise investigational product may be resumed unless otherwise contraindicated.

Patients who use an HMG-CoA-reductase inhibitor (a 'statin') will be advised to promptly report muscle pain, tenderness or weakness, and discontinue the statin if signs or symptoms appear. The statin should be discontinued if markedly elevated CK levels occur, for instance CK >5xULN. CK elevations that are greater than 3xULN but less than 10xULN need to be confirmed by a repeated measurement preferably within one week, after which a decision is made to discontinue the statin treatment, or resume the treatment, perhaps at a lower dose, according to country-specific guidelines.

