6.3 Efficacy

| Table 7 | Efficacy laboratory variables | | | | | | | | | | |
|------------|-------------------------------|----|----|----|---|---|---|---|----|----|----|
| Visit | S | 1 | 2 | 3 | 4 | 5 | 6 | 7 | 8 | 9 | 10 |
| Study Week | -7 | -5 | -4 | -1 | 0 | 1 | 4 | 8 | 12 | 16 | 20 |
| HbA1c | Х | Х | | Х | Х | | Х | Х | Х | Х | |
| FPG | | Х | Х | Х | Х | Х | Х | Х | Х | Х | Х |

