11.2.2 Last observation carried forward (LOCF)

If no measurement is available at a time point, the last post-baseline measurement prior to the specific time-point will be used instead for analysis.

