12.1.2 Full Analysis Set

The Full Analysis Set will include all randomised subjects (as randomised) who received at least one dose of double-blind study medication and who have a non-missing baseline value and at least one post-baseline value for at least one efficacy variable. The intention-to-treat principle will be preserved despite the exclusion of subjects who took no study medication, as the decision of whether or not to begin treatment during the randomised treatment period could not be influenced by knowledge of the assigned treatment. All efficacy analyses will be based on the Full Analysis Set.

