12.2 Methods of statistical analyses

All efficacy analyses will be based on the Full Analysis Set. The primary efficacy variable of change from baseline in HbA1c will also be analyzed using the Per-Protocol Analysis Set if more than 10% of the subjects in any regimen are found to significantly violate the terms and

conditions of the protocol (see description of Per-Protocol Analysis Set). Treatment effects will be determined through pair-wise treatment group comparisons: each dapagliflozin dose group versus placebo. No statistical comparisons will be made amongst the three dapagliflozin groups (2.5 mg BID, 5 mg BID and 10 mg QD).

The dapagliflozin 10 mg QD treatment group is provided as a measure of assay sensitivity. Comparisons of dapagliflozin 10 mg QD to placebo will be performed with nominal p values, outside of the controls, for multiplicity for the two dapagliflozin BID groups.

For efficacy variables, missing values at week 16 will be replaced by the last observation carried forward (LOCF) approach (see 11.2.2).

The primary objective of the study is to assess the efficacy of dapagliflozin 2.5 mg BID and 5 mg BID compared to placebo as add-on therapy to metformin in improving glycaemic control in subjects with type 2 diabetes, as determined by the primary efficacy variable change in HbA1c from baseline to week 16.

The null hypotheses H_{01} and H_{02} given below will be tested against the alternative hypotheses H_{A1} and H_{A2} respectively ($\alpha \le 0.050$, two-sided):

| $H_{01}: \mu_{D1} - \mu_P = 0,$ | H ₀₂ : $\mu_{D2} - \mu_P = 0$, |
|-------------------------------------|--|
| $H_{A1}: \mu_{D1} - \mu_P \neq 0,$ | $H_{A2}: \mu_{D2} - \mu_P \neq 0,$ |

where μ_{D1} and μ_{D2} denote the mean change in HbA1c from baseline to week 16 in the two dapagliflozin dose groups (2.5 mg BID and 5 mg BID) and μ_P denotes the mean change in HbA1c from baseline to week 16 in the placebo group. D1 denotes the dapagliflozin 2.5 mg BID dose group, and D2 denotes the dapagliflozin 5 mg BID dose group

The following key secondary efficacy variables have been identified:

- 1. Percent change in body weight from baseline to week 16
- 2. Change in FPG from baseline to week 1
- 3. Change in FPG from baseline to week 16
- 4. Proportion of patients with HbA1c<7.0%, in patients with HbA1c \geq 7.0% at baseline.

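### LOCF on the week-16 HbA1c <7.0% responder endpoint scores some early leavers as successes and leaves a few Full Analysis Set patients with no responder status; a non-responder analysis should be stated beside it

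*Protocol*

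**What the plan says.** Section 12.2 sets one missing-data rule for efficacy variables: "missing values at week 16 will be replaced by the last observation carried forward". Section 11.2.2 defines it: if a value is absent, "the last post-baseline measurement prior to the specific time-point will be used instead for analysis". Baseline is thus never carried forward.

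The same section lists four key secondary variables. The fourth is the HbA1c target proportion, which the Synopsis ties to a time point: "Proportion of patients with HbA1c<7.0% at week 16, in patients who had HbA1c" at or above 7.0% at baseline. It is formally tested, at 0.05 within each BID dose stream, as the last step of the fixed sequence. The text on analysing proportions names the estimation method and a Fisher's exact fallback, but gives no rule for patients without a week-16 value.

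Three other provisions decide who is affected:

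- Section 12.1.2 admits a patient to the Full Analysis Set with a baseline value and "at least one post-baseline value for at least one efficacy variable". That variable need not be HbA1c.
- Table 7 in Section 6.3 schedules FPG from week 1 but post-baseline HbA1c only at weeks 4, 8, 12 and 16, with none at the follow-up visit.
- Section 4.3.2 deals with early exit: "Randomised patients who discontinue the study before week 16 should return and complete the procedures described for Visit 9", within 7 days of stopping. Visit 9 includes HbA1c.

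**The concern.** Section 4.3.1 treats discontinuation as leaving both study treatment and assessments, so an early leaver will normally have no HbA1c at week 16. LOCF fills the gap with a value from around the time of stopping. If that value is below 7.0%, someone who stopped for an adverse event, say at week 5, is recorded as being at target on treatment at week 16.

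The denominator raises a second issue. A patient with a week-1 FPG who leaves before the week-4 HbA1c and does not return for the Visit 9 procedures belongs to the Full Analysis Set but has no HbA1c to carry. No rule classifies that patient, and in practice the record would fall out of the calculation. That fits poorly with the statement in 12.1.2 and 12.2 that all efficacy analyses use the Full Analysis Set.

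Within one arm, LOCF cannot give a lower responder rate than counting these patients as failures: it can only add successes or shrink the denominator. At stake is a formally tested between-arm difference for which the protocol states no second analysis. The parallel observed-data and LOCF summaries in 12.2 are for continuous variables, and the per-protocol repeat in 12.1.3 covers only the primary variable.

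**Working it through.** **The protocol's own figures.** It gives none for this endpoint. Its sample size (Section 12.3) reproduces: for a difference of 0.5%, SD 0.97% and two-sided 0.025, the exact t-test has power 0.898 at 94 per group and 0.901 at 95, hence 95. Then 95/0.97 = 97.9, rounded up to 98, and 4 × 98 = 392. None of this changes below.

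**Inputs from the protocol.** 98 per arm (12.3), with a 20% cap on the HbA1c <7.0% stratum (3.1.1.4): 0.80 × 98 = 78.4, so about 78 per arm in the subset if the cap is filled, and up to 98 if that stratum is empty. This is approximate, because the stratum uses the Visit 3 value and the endpoint uses baseline.

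**Assumptions.** 5% to 15% leave early. Completers respond at 20% on placebo and 40% on a dapagliflozin dose. Leavers have a last HbA1c below 7.0% at the same rates as completers in their arm.

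**Carried successes.** Let d be the share leaving and f the share of leavers with a last value below 7.0%, with D for dapagliflozin and P for placebo. If everyone has some post-baseline HbA1c:

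shift in the difference (LOCF minus non-responder) = d_D × f_D − d_P × f_P

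| Leaving, placebo | Leaving, dapagliflozin | LOCF difference | Non-responder difference | Shift (points) |
|---|---|---|---|---|
| 5% | 5% | 20.0 | 19.0 | +1.0 |
| 10% | 10% | 20.0 | 18.0 | +2.0 |
| 15% | 15% | 20.0 | 17.0 | +3.0 |
| 5% | 15% | 20.0 | 15.0 | +5.0 |
| 15% | 5% | 20.0 | 21.0 | −1.0 |

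For example, the third row is 0.15 × 0.40 − 0.15 × 0.20 = 0.030, and the last is 0.05 × 0.40 − 0.15 × 0.20 = −0.010. If leavers respond at only half the completer rates (20% and 10%), equal dropout gives 0.05 × 0.10 = 0.5 to 0.15 × 0.10 = 1.5 points.

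**Scale.** SE = √(0.4 × 0.6/78 + 0.2 × 0.8/78) = √(0.40/78) = 0.072, or 7.2 points. With equal dropout the shift is 1.0/7.2 = 0.14 to 3.0/7.2 = 0.42 SE.

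**Denominator.** Suppose 3% per arm have no post-baseline HbA1c. The figure is borrowed from 12.3, where it covers patients lacking usable efficacy measurements, so it indicates only an order of magnitude. That is 0.03 × 78 = 2.3 patients per arm. Counting them as failures, with no other dropout, turns 20.0 points into 0.97 × 20.0 = 19.4, a shift of 0.6 points or 0.08 SE.

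**Both together.**

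- 10% leaving in each arm: 0.87 × 40% = 34.8% versus 0.87 × 20% = 17.4%, a difference of 17.4 instead of 20.0 points. Power at two-sided 0.05 is 0.70 instead of 0.77.
- 5% leaving placebo and 15% leaving dapagliflozin: 0.82 × 40% = 32.8% versus 0.92 × 20% = 18.4%, a difference of 14.4 points. Power is 0.54 instead of 0.77.

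Across all scenarios the shift runs from −1.0 to +5.6 points.

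**The case against.** The strongest reply is that direction and size rest on invented dropout and response rates, and that the protocol already limits the damage. Much of this stands.

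- A reader might infer that LOCF must favour dapagliflozin. The documents do not support that: no dropout rates are given, and heavier placebo loss reverses the sign.
- A reader might put the shift as high as 4.5 points with equal dropout: 0.15 × (0.50 − 0.20). That needs dapagliflozin leavers to respond at 50%, better than the 40% assumed for their own arm. At 40% versus 20% the ceiling is 3.0 points.
- A reader might infer that patients removed for poor control become successes. Section 3.1.1.4 does say "Subjects who lack glycaemic control as defined below will be discontinued from the study", but they leave with central-laboratory FPG above 200 to 270 mg/dL, depending on the period. Few will have a last HbA1c below 7.0%, so LOCF already scores nearly all of them as failures.
- The Visit 9 sample at exit means the carried value is usually an end-of-treatment measurement, not a stale one. It also makes patients with no post-baseline HbA1c rare. Their loss from the denominator is inferred from 11.2.2, 12.1.2 and Table 7; no section states it.
- Counting missing as failure is also a single-value rule and is not neutral: in the last row of the table it widens the difference.
- The endpoint comes last in its sequence, so nothing tested later depends on it.

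What does not stand is the argument that this is merely detail for the SAP. The SAP is not shown and may add a sensitivity analysis, but the protocol itself fixes LOCF for this endpoint. A fresh measurement at exit still describes the time of stopping and not week 16.

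**Conclusion.** The point holds in a limited form. As written, the protocol counts an early leaver with a last post-baseline HbA1c below 7.0% as a week-16 responder, and gives no responder status to the few Full Analysis Set patients without any post-baseline HbA1c. Responder rates in each arm can be overstated. The treatment difference can move either way, and most plausibly moves towards dapagliflozin when dropout is similar across arms or higher on active drug.

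Under equal dropout the likely size is modest, at about 1 to 3 points. It approaches a level that could change the test result only if dapagliflozin loses clearly more patients than placebo. Only the figure of about 78 per arm comes from the protocol, and it presumes that the low-HbA1c stratum fills. The matter is worth correcting because the endpoint is formally tested and has no stated second analysis. It does not touch the primary conclusion. The working supports no similar claim about the systolic blood pressure proportion, and it does not show that LOCF must be abandoned.

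**What to change.** In Section 12.2, add for key secondary 4 an analysis that:

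- keeps every Full Analysis Set patient with baseline HbA1c at or above 7.0% in the denominator;
- counts as non-responders those who discontinued before week 16 and those with no post-baseline HbA1c;
- says that a Visit 9 value obtained at early exit does not count as a week-16 value.

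Defining failure by discontinuation, and not simply by a missing sample, avoids failing a patient who stayed on treatment but missed the week-16 blood draw and has an earlier post-baseline value. Report the analysis beside the LOCF result, at minimum as a named sensitivity analysis.

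The cost is a short addition to the text, one extra table and slightly lower responder rates. Visits, sampling, sample size and the primary analysis stay as they are.

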A Hochberg procedure will be used to control the overall Type I error rate for the two treatment group comparisons (dapagliflozin 2.5 mg BID and 5 mg BID) versus placebo for the primary efficacy variable. Further testing of treatment group(s) versus placebo for key secondary variables will be performed using a hierarchical, fixed sequence testing procedure, but only with respect to the treatment group(s) found significant for the primary efficacy variable.

The sample size for this study was selected to demonstrate a difference in the mean change in HbA1c from baseline to week 16 between one of the dapagliflozin treatment groups (2.5 mg BID and/or 5 mg BID) versus placebo in combination with metformin. A review of variability estimates from BMS studies MB102013 and MB102014 suggests that the standard deviation associated with change in HbA1c from baseline to week 16 using LOCF will not be more than 0.97%. Since the overall Type I error will be controlled for the two treatment comparisons using a Hochberg procedure, sample size estimation is based on the conservative assumption that one dose comparison may not reach statistically significance. In this situation, in order to detect a 0.5% difference in mean change from baseline in HbA1c between one of the dapagliflozin treatment groups (2.5 mg BID or 5 mg BID) versus placebo using a 2-sample t-test at a 0.025, two-sided significance level with 90% power, 95 evaluable patients are required per treatment group in the Full Analysis Set. If one assumes 3% of the subjects will not have a baseline and post-baseline efficacy measurement, 98 subjects per group (392 total subjects) will need to be randomised.

Further, if 40% of subjects fail to meet entry criteria for randomisation (as seen in study MB102014), then approximately 654 subjects must be enrolled.

TABLE OF CONTENTS

PAGE

| | TITLE PAGE | 1 |
|------------------------------------|--|----------|
| | PROTOCOL SYNOPSIS | 2 |
| | TABLE OF CONTENTS | 9 |
| | LIST OF ABBREVIATIONS AND DEFINITION OF TERMS | 14 |
| 1. | INTRODUCTION | 16 |
| 1.1 | Background | 16 |
| 1.2 | Research hypothesis | 17 |
| 1.3 | Rationale for conducting this study | 17 |
| 1.4 | Benefit/risk and ethical assessment | 18 |
| 2. | STUDY OBJECTIVES | 20 |
| 2.1 | Primary objective | 20 |
| 2.2 2.2.1 2.2.2 | Secondary objectives Key Secondary Objectives Other Secondary Objectives | 21 |
| 2.3 | Safety objective | 22 |
| 2.4 | Pharmacogenetic Objective | 22 |

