A Hochberg procedure will be used to control the overall Type I error rate ≤ 0.050 for the two treatment group (2.5 mg BID and 5 mg BID) comparisons versus placebo for the primary efficacy variable (Hochberg 1988). Nominal p-values for the differences between the two dapagliflozin dose groups (2.5 mg BID and 5 mg BID) and the placebo group will be determined. If the largest of the two p-values is ≤ 0.050 (two-sided), then the two treatment group comparisons (2.5 mg BID and 5 mg BID) versus placebo will be declared statistically significant. If the largest of the p-values is ≥ 0.050 (two-sided), then the corresponding

treatment group comparison (2.5 mg BID or 5 mg BID) versus placebo is not significant. Then, the smaller p-value will be assessed for significance at a 0.025 level (two-sided).

Further testing of treatment groups (2.5 mg BID and/or 5 mg BID) versus placebo for key secondary variables will be performed using a hierarchical, fixed sequence testing procedure, but only with respect to the treatment group(s) found significant for the primary efficacy variable. The testing of the key secondary variables will be performed in the order listed above. The level of significance used for key secondary variables will be 0.050. The testing procedure is described below.

If at least one of the comparisons between a dapagliflozin treatment group (2.5 mg BID and/or 5 mg BID) and the placebo treatment group is significant for the primary efficacy variable, all statistical tests for the key secondary efficacy variables will be performed and nominal p-values will be reported. However, in order to protect the global type I error rate of the hierarchical testing procedure, the interpretation of the statistical significance of treatment comparisons for each key secondary efficacy variable will be done using a step-wise procedure. Within each dose group (2.5 mg BID and/or 5 mg BID) that was significantly superior to placebo for the primary efficacy variable, testing of key secondary variables will be performed in a fixed order sequence (see above). The testing sequence will be applied separately for each dose group (2.5 mg BID and/or 5 mg BID) with an α =0.05 for each testing stream. Inference for hypothesis testing for the key secondary objectives will stop at the first occurrence of a failed test using the order stated above for, regardless of how testing has progressed in the other dose group.

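### Section 12.2 says the step-wise testing protects the global type I error rate, but the two BID doses run unlinked key-secondary sequences at 0.05 each, so error is controlled for the primary family and within each dose, not across both

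*Protocol*

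**What the plan says.** Section 12.2 of the protocol sets out three steps.

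- **Primary variable.** "A Hochberg procedure will be used to control the overall Type I error rate ≤ 0.050 for the two treatment group" comparisons with placebo on HbA1c (2.5 mg BID and 5 mg BID). If the larger p-value is at most 0.050, both doses are significant. Otherwise the smaller one is tested at 0.025.
- **Key secondary variables.** A dose that passes goes on to percent change in weight, FPG at week 1, FPG at week 16 and the proportion reaching HbA1c <7.0%, in that order. On the level: "The level of significance used for key secondary variables will be 0.050". On the structure: "The testing sequence will be applied separately for each dose group", "with an α =0.05 for each testing stream". Testing in a dose stops at its first failure, "regardless of how testing has progressed in the other dose group".
- **Purpose.** Significance is to be interpreted step-wise "in order to protect the global type I error rate of the hierarchical testing procedure".

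The 10 mg QD arm is outside this scheme and is tested with nominal p-values.

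**The concern.** A fixed sequence at 0.05 controls error within that one sequence. Here there are two, one per dose, and nothing connects them. Hochberg has already used 0.05 on the primary pair, and a dose that wins alone at 0.025 still opens its sequence at 0.05. No alpha is divided between the doses or carried from primary to secondary. The stated purpose and the stated rule therefore disagree.

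At stake are the eight key secondary hypotheses (four variables, two doses). They are singled out in advance in section 2.2.1 and given formal inference in a study that section 3.1 calls pivotal. As written, a reader would take any significant result among them as covered by one 5% error rate shared with the primary tests.

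**Working it through.** **Inputs from the protocol.** Difference 0.5%, SD 0.97%, two-sided 0.025, 90% power, 95 evaluable per group, 3% not evaluable (section 12.3); allocation 1:1:1:1 (section 3.1); testing rules (section 12.2). The protocol gives no numerical overall error rate, so only the sample size can be reproduced.

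**The plan's own figure.** A two-sample t-test with these inputs gives 90.1% power at 95 per group (89.8% at 94). 95/0.97 rounds up to 98, and 4 × 98 = 392. This agrees with the protocol. The expected test statistic at the planned effect is 0.5/(0.97 × √(2/95)) = 3.55.

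**Correlation.** With equal arms and a shared placebo group, the two dose-versus-placebo statistics on one variable have covariance σ²/n and variance 2σ²/n each, so their correlation is 0.5.

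**Direct calculations, primary effects so large that the sequences always open:**

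- Same key secondary null in both doses: 1 − P(|Z1| < 1.96 and |Z2| < 1.96) at correlation 0.5 = 9.07%.
- If the two sequences were independent: 1 − 0.95² = 9.75%. Upper bound: 0.05 + 0.05 = 10%.
- One dose null on HbA1c, the other strongly effective with a null first secondary: Hochberg tests the null dose at 0.05 and the effective dose's sequence is open at 0.05. With independence, 0.05 + 0.95 × 0.05 = 9.75%.

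**Simulation of the whole procedure** (Hochberg, then the fixed sequences; at least one million trials per scenario). The correlation between endpoints is not in the protocol. It is assumed to be 0.3 unless stated.

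| Truth | Chance of at least one false rejection |
|---|---|
| Nothing works (global null) | 4.8% |
| Both doses at planned HbA1c effect, secondaries null | 8.2% (8.5% at endpoint correlation 0; about 7.6% at 0.5) |
| One dose at planned effect, other null on HbA1c, secondaries null | 8.7% (9.0% at endpoint correlation 0) |
| Both HbA1c effects large, secondaries null | 9.1% |
| Both large, first true null at a different variable in each dose | 9.7% |
| One HbA1c effect large, other null, secondaries null | 9.7% |

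**Would halving the sequence level be enough?** With both primary effects real, sequences at 0.025 give 4.2% to 4.9%. With one dose null on HbA1c and the other strongly effective, Hochberg still spends 0.05 on the null dose: 0.05 + 0.95 × 0.025 = 7.4% (simulated 7.3%). So it is not enough.

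**A chain that does control the rate.** Give each dose 0.025 down its own sequence of five hypotheses, and pass it to the other dose only when all five are rejected. The starting levels sum to 0.025 + 0.025 = 0.05, and the simulated rates were at or below 5.0% in every scenario tried.

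**Price of the chain at the planned effect in both doses.** At least one primary success: 97.3% now, 97.0% under the chain. Both succeed: 90.3% now; under the chain 84.0% if a dose never completes its sequence, 87.0% if it does so half the time, 89.9% if always.

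**The case against.** The best defence is that the design is openly per dose. Section 12.2 says the sequences are separate, states 0.05 for each, and says one does not depend on the other. Whether two doses' secondary claims must share one 0.05 is partly a choice of error family. That stands as a defence of the rule, but not of the sentence that calls the protection global. The primary variable is also adjusted across doses, so the plan itself treats the doses as one family there.

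A second point is direction. The rates above count two-sided errors. With both doses effective on HbA1c and weight null, the chance of a false claim of benefit is about 4.3-4.6%. This limits the practical harm. It does not restore the stated property, since the plan's tests and levels are two-sided.

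Three stronger readings are tempting and are not supported:

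- A reader might infer that this trial's error rate simply is 9-10%. That is the worst case, which needs a well-powered true HbA1c effect in at least one dose together with true nulls elsewhere. Under the global null the rate is below 5%.
- A reader might infer that the primary result is compromised. It is not. Hochberg is stated for the primary pair and controls it, and the sample size rests on that test.
- A reader might take the synopsis to make the same mistake. Its Hochberg sentence claims control for the primary comparisons only, and that is correct.

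**Conclusion.** The point holds for the key secondary claims. The procedure controls the two primary comparisons at 0.05, and error within each dose's sequence at 0.05, but not the global rate that section 12.2 says it protects. Over primary plus key secondary hypotheses the familywise rate is about 8-9% at the planned HbA1c effect (roughly 7.6% to 9% for endpoint correlations of 0 to 0.5), up to 9-10% in the worst case, and about 4.8% under the global null. The figures rest on correlation 0.5 between doses, which follows from the allocation, and on assumed correlations between endpoints. The 9.07%, 9.75% and 10% figures need no such assumption for two open sequences. The SAP is not at hand, but the protocol is explicit on this rule, so the text needs correcting here.

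**What to change.** **Minimum.** In section 12.2, replace the wording on global protection with a statement that Hochberg controls the two primary comparisons at 0.05, and that key-secondary error is controlled at 0.05 within each BID dose only, not across doses. Carry the same statement into the SAP before unblinding. This costs one paragraph and changes no test, power or sample size.

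**If global control is wanted.** Use a gatekeeping or graphical procedure over all 10 hypotheses (two doses, five variables). One example is the chain above: 0.025 per dose through HbA1c, weight, FPG week 1, FPG week 16 and HbA1c <7.0%, passed on only after the whole sequence is rejected. The sample size and the 90% single-dose power are unchanged, because section 12.3 already uses 0.025. The chance of at least one primary success hardly moves.

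It is still a real trade-off. The chance that both doses succeed on HbA1c falls from 90.3% to between 84% and 90%, and key secondary tests start at 0.025 rather than 0.05. Where in that range it lands depends on how often a sequence is completed. The protocol gives no power for any key secondary, and the last one is a responder variable in the subset with baseline HbA1c ≥7.0%. The sponsor should choose knowingly between this and the rewording.
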